### Sensitivity Analysis

Inclusion criteria for Part B of the Qualification Phase include having a peak score ( $E_{max}$ ) on the Drug Liking VAS greater than that of placebo by at least 15 points in response to 12 mg hydromorphone. In order to assess the robustness of this 15-point difference, a sensitivity

analysis will be conducted in the Treatment Phase to assess the null hypothesis that the mean difference in Drug Liking VAS  $E_{max}$  between the positive controls, hydromorphone 8 and 16 mg, and placebo is less than or equal to 15 against the alternative hypothesis that the mean difference in Drug Liking VAS  $E_{max}$  between hydromorphone and placebo is greater than 15. The hypothesis can be expressed as:

$$H_0: \mu_c - \mu_p \leq 15 \text{ versus } H_a: \mu_c - \mu_p > 15$$

#### 8.1.4 Analysis of Pharmacokinetics

Pharmacokinetic analyses will be performed using the Dose Selection PK population in Part A and the PK population in Part B.

The PK parameters for plasma nalbuphine and (Part A only) its metabolites will be calculated using non-compartmental analysis and will be summarized by dose level in Part A and by treatment in Part B. Graphs of the concentration (original and log transformed) versus time will be generated. Descriptive statistics, including n, mean, SD, coefficient of variation (CV), minimum, median, and maximum will be calculated by dose level (Part A) and treatment (Part B) and time point for each study drug. Concentrations below the limit of quantification (BLQ) will be set to zero for the generation of summary statistics for concentrations and the generation of mean concentration-time plots.

For the calculation of the PK parameters, concentration-time data will be treated as follows: BLQ concentrations before the first quantifiable concentration will be set to zero; BLQ concentrations after the first quantifiable concentration will be treated as missing; and pre-dose sampling times relative to dosing will be set to zero. Descriptive statistics, including n, mean, SD, geometric mean, geometric CV, minimum, median, and maximum, will be calculated by dose level and treatment group for all PK parameters except  $T_{max}$ ,  $t_{1/2}$ , and kel. Time to maximum observed plasma concentration data will be summarized with minimum, median, maximum, Q1 and Q3. The  $t_{1/2}$  and kel data will be summarized with n, mean, SD, CV, minimum, median, and maximum.

PK profiles will be analyzed for all subjects, even if some PK sampling time points are missed. The PK parameters will be subject to quality control criteria. If quality control criteria are met, the PK parameters will be used in analyses and models. Quality control criteria for PK will be sufficient to eliminate unreliable data. Details will be provided in the SAP.

The PK parameters summary will be presented separately for a subset (if applicable) of subjects who do not vomit within 12 hours of dosing in Part A and Part B of the study.

#### 8.1.5 Analysis of Safety Assessments

For Part A, the analysis of safety assessments will be performed using the Dose Selection Safety population. For Part B, the analysis of safety assessments will be performed using the Safety population.

Assessment of safety will be based on the incidence of AEs, AEs resulting in discontinuation, and SAEs by treatment. AE summaries will be provided showing the number and percentage of subjects who experienced at least one AE. AEs will also be tabulated by maximum severity and

by maximum relationship to study drug. These summaries will be presented by body system and preferred term (Medical Dictionary for Regulatory Activities [MedDRA] 20.0 or higher). SAEs and AEs resulting in discontinuation will be summarized separately. Adverse event data from the Qualification Phase will be listed by subject for the Randomized population but not summarized further.

Clinical laboratory data collected during the Treatment Phase will be summarized by the type of laboratory test and visit. Descriptive statistics (mean, SD, minimum, median and maximum) and the number of subjects with laboratory test results below, within, and above normal ranges will be tabulated by visit. Abnormal findings in laboratory data will be listed.

Treatment Phase vital signs (blood pressure, respiratory rate, heart rate, SpO2) will be analyzed as minimum, maximum, and final post-dose values, since the analyses of these extremes are more meaningful than analyses of individual time points.

The ECG data (absolute values in heart rate and the PR, QRS, QT, QTcB and QTcF intervals) will be summarized using descriptive statistics for data collected in the Treatment Phase.

Physical examination abnormal results will be listed by subject and visit. Baseline and since last visit C-SSRS results will be listed. No summaries will be provided.

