## **4.5 Qualification Criteria (Part B)**

Subjects must meet the following qualification criteria to be eligible to enter the Treatment Phase:

1. Peak score ( $E_{max}$ ) of  $\geq 65$  on the Drug Liking VAS and greater than that of placebo by at least 15 points in response to 12 mg hydromorphone.
2. Drug Liking VAS scores over time that are consistent with the known pharmacology of 12 mg hydromorphone.
3. Acceptable placebo response on Drug Liking VAS (score between 40 and 60, inclusive).
4. Ability to complete the PD assessments and have acceptable overall responses for placebo and hydromorphone based on all other measures that are consistent with the known pharmacology of the drugs administered, as judged by the investigator or designee.
5. Able to tolerate 12 mg hydromorphone, as judged by the investigator or designee based on available safety and PD data (eg, no episodes of vomiting within the first 4 hours post-dose).
6. General behavior suggests that the subject could successfully complete the study, as judged by the research site staff.

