  - Admission to any Treatment Period in Part B: Subjects who have a positive urine drug screen and a COWS score < 5 may be rescheduled at the discretion of the investigator or designee. If benzodiazepines or THC are positive, inclusion will be at the discretion of the investigator, for example, if drug levels are stable at low concentrations or decreasing due to the long half-lives of parent compounds and/or metabolites. THC levels that have increased from the time of the last visit may be acceptable, at the discretion of the investigator or designee, provided that there are no visible signs of impairment and/or intoxication due to THC exposure (eg, euphoria, dry mouth, slowed reflexes, excessive drowsiness, increased appetite, red eyes, paranoia, anxiety, hallucinations, tachycardia, emitting odor of marijuana).
- COWS score  $\geq 5$ . Subjects will be medically managed for at least 4 hours or longer until the investigator determines that the subject can be safely discharged from the CRU.
- Positive breath alcohol test at admission to the Dose Selection Phase in Part A or Qualification Phase or any Treatment Period in Part B. Subjects with a positive result at Screening or admission to any visit may be rescheduled at the discretion of the investigator or designee.
- Termination of the study
- Subject did not meet the qualification criteria outlined in Section 4.5.
- Dose escalation (Part A) has been stopped according to the criteria outlined in Section 4.9.

When an event such as a family emergency, a transient intercurrent illness (such as a cold) unrelated to study drug, or a remediable act of non-compliance prevents a subject from participating in a scheduled visit, but the subject wishes to continue in the study, with the

permission of the sponsor/medical monitor and in consultation with the investigator the research site staff may attempt to reschedule the visit and retain the subject in the study.

If a subject is prematurely discontinued from participation in the study for any reason after study drug administration, the investigator or designee must make every effort to perform the assessments scheduled for the Follow-up visit. The reason for withdrawal will be recorded in the case report form (CRF) and the subject's source medical record.

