##### 8.1.1.2 Qualification and Treatment Phase (Part B)

- *Qualification Safety Population*: All subjects who receive at least one dose of study medication during the Qualification Phase.
- *Randomized Population*: All subjects who are assigned a randomization number in the Treatment Phase.
- *Safety Population*: All randomized subjects who receive any study treatment in the Treatment Phase.

- *Completers Population:* All subjects in the Safety population who receive all study treatments and complete all treatment periods in the Treatment Phase regardless whether they have protocol deviations. Subjects must have at least one response on Drug Liking VAS within 2 hours of  $T_{max}$  for each treatment in the study.
- *PK Population:* All subjects in the Randomized population who receive at least 1 dose of nalbuphine from whom at least 1 PK sample is obtained after dosing, and who have no protocol deviations or other circumstances that would exclude the subjects from analysis.

Details of subject evaluability criteria will be determined prior to study unblinding.

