### 8.1.3 Planned Analyses of Primary and Secondary Pharmacodynamic Assessments (Part B)

PD data will be analyzed for the Completers population. The primary endpoint is Drug Liking VAS  $E_{max}$ , and the key secondary endpoints are Overall Drug Liking VAS  $E_{max}$ , and Take Drug Again VAS  $E_{max}$ .

For the Qualification Phase, Drug Liking VAS  $E_{max}$  will be summarized by treatment and paired difference for the Completers population using descriptive statistics.

For the Treatment Phase, PD data at each time point will be summarized by descriptive statistics including mean, standard error (SE), minimum, first quartile (Q1), median, third quartile (Q3) and maximum. PD data will be presented graphically (where appropriate) for the Completers population. Derived endpoints will be summarized by treatment and paired difference using descriptive statistics. PD endpoints will be provided in both tables and figures (as applicable). Outliers will be listed by measure and parameter.

PD endpoints for the Treatment Phase ( $E_{max}$ ,  $E_{min}$ , and TA\_AUE, as appropriate) will be analyzed using a mixed-effect model if the distribution of the residuals is normally distributed. The model will include treatment, period, sequence and first-order carryover effect (where applicable) as fixed effects, baseline (pre-dose) measurement as a covariate (where applicable), and subject nested within treatment sequence as random effect. First, the residuals from each mixed-effect model, excluding carryover effects, will be investigated for normality using the Shapiro-Wilk W-test. Parameters will be analyzed under the assumption of a normal distribution if the  $P$  value of the test is  $\geq 0.01$ .  The null and alternative hypotheses for this analysis are shown below:

$H_0$ : The distribution of residuals is normal versus  $H_a$ : The distribution of residuals is not normal

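### Subjects dosed in the Qualification Phase but not randomized appear in no planned adverse event output, although a population that includes them is defined

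*Protocol*

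**What the plan says.** Protocol 8.1.5 sets two rules for Part B. The general one is "For Part B, the analysis of safety assessments will be performed using the Safety population". The one specific to the Qualification Phase is "Adverse event data from the Qualification Phase will be listed by subject for the Randomized population but not summarized further".

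The populations are in Protocol 8.1.1.2. The Randomized Population is "All subjects who are assigned a randomization number in the Treatment Phase". The Safety Population is the part of that group dosed in the Treatment Phase. The Qualification Safety Population is "All subjects who receive at least one dose of study medication during the Qualification Phase", with no condition about later randomization.

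Entry to the Treatment Phase depends on Protocol 4.5. Item 5 requires that the subject tolerate 12 mg hydromorphone in the investigator's judgement, and its example is "no episodes of vomiting within the first 4 hours post-dose". Protocol 4.8 includes in its discontinuation circumstances "Subject did not meet the qualification criteria outlined in Section 4.5".

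Protocol 9.2 provides for database entry of demographic data for subjects who do not qualify and does not mention their AEs. The supplied SAP covers Part A only (SAP 2.1 and 5).

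**The concern.** Everyone in the drug discrimination test receives blinded study drug: an opioid dose, placebo, or both if they stay for both days. Those who then qualify and are randomized have their Qualification AEs listed; those who are not randomized do not. Because intolerance of hydromorphone is a reason for not qualifying, an AE can be what removes the subject from the listing of AEs. A subject failed for early vomiting would leave no trace of that vomiting in any planned output.

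At stake is the completeness of the reported AE record for hydromorphone 12 mg and placebo in this phase. A reader of the listing would see only subjects who had passed a tolerability screen and would probably take it as the experience of everyone dosed.

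**Working it through.** **Step 1. Trace a dosed, non-randomized subject through the Part B outputs.**

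| Planned output | Population | Includes the subject? |
|---|---|---|
| Qualification AE listing (8.1.5) | Randomized | No: no Treatment Phase randomization number |
| Part B AE summaries, including the separate SAE and discontinuation-AE summaries (8.1.5) | Safety | No: not randomized, not dosed in the Treatment Phase |
| Qualification Drug Liking summary (8.1.3) | Completers | No, and it is not an AE output |
| Demographics and baseline (8.1.8) | Randomized | No, and it is not an AE output |

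The subject belongs to the Qualification Safety Population, but none of these outputs uses it. In Part A, by contrast, the definition of the Dose Selection Safety Population (8.1.1.1) states that its members enter the safety analysis. The SAP's populations and output indexes are confined to Part A, so they add nothing for Qualification.

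**Step 2. The number randomized.** Protocol 8.2 plans 42 completers with about 25% dropout: 42 / (1 − 0.25) = 56, which matches the stated 56. This figure is not in dispute; it is used only to size the group left out.

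**Step 3. An illustrative size for that group.** The documents give no AE or intolerance rate for Qualification. The nearest figure is in Protocol 3.2: at the former site, roughly 40% to 60% of history-qualified subjects did not adequately discriminate the test drug or report its positive effects. Call this fraction *f* and assume it carries over.

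- Dosed in Qualification = 56 / (1 − *f*), rounded up
- Outside the listing = dosed − 56
- Share covered = 56 / dosed

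| *f* | Dosed | Outside the listing | Share covered |
|---|---|---|---|
| 0.40 | 93.3, so 94 | 38 | 59.6% |
| 0.50 | 112 | 56 | 50% |
| 0.60 | 140 | 84 | 40% |

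These are counts of dosed subjects, not of subjects with AEs. The rate does not describe tolerability failures and comes from a site that has since closed.

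**The case against.** The strongest reply is that 8.1.5 makes a deliberate and unambiguous reporting choice of little consequence. The safety objective concerns nalbuphine, which is not given in Qualification. Hydromorphone AEs are summarized in the Treatment Phase at 8 mg and 16 mg, on either side of the 12 mg Qualification dose. No endpoint or decision rule uses AEs from non-qualifiers. All AEs are recorded in source (Section 7), SAEs are reported within 24 hours (7.3.1), AEs leading to discontinuation are followed up (7.4), and the withdrawal reason goes into the CRF (4.8). This stands, and it keeps the point minor. It does not supply a planned table or listing for these subjects.

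A second reply is that 8.1.2 leaves population detail to a SAP, and no Part B SAP is available. That weakens any complaint that the Qualification Safety Population has no use yet: a later SAP could assign one. It does not undo the explicit 8.1.5 sentence, and a Part B SAP that followed that sentence would repeat the gap.

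Three smaller objections are fair:

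- Section 9.2 does not say that only demographic data are entered, so the inference about AEs rests on silence.
- Using Completers for Drug Liking is weak evidence, since a safety population would not be expected for a pharmacodynamic summary.
- Item 5 of 4.5 is a judgement with vomiting as an example, so the text shows that a subject can be excluded because of an AE, not how often this happens.

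**Conclusion.** The concern holds, as a minor point. On the protocol's own definitions, a subject dosed in Qualification and not randomized is in no AE output planned in the supplied documents, and the omission can be related to tolerability. This follows from the text and needs no numerical assumption.

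The size in AE terms is unknown. The range of 38 to 84 subjects is illustrative only and rests on two assumptions: that 56 are randomized, and that the former site's discrimination failure rate applies at the new one.

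The effect is confined to the Qualification AE record for hydromorphone and placebo. The nalbuphine comparisons, the primary analysis and the sample size are untouched.

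**What to change.** Before Part B starts:

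1. In Protocol 8.1.5, change the population for the Qualification Phase AE listing from Randomized to Qualification Safety, and list by subject and treatment received. Treatment will be known, because 5.5.2 has the Qualification codes unblinded after each group.
2. In Protocol 9.2, add Qualification dosing and AE data to what is entered for subjects who do not qualify. The withdrawal reason is already covered by 4.8.
3. Carry the same population into the Part B SAP.

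The cost is two protocol sentences, some extra database entry of AEs already held in source, and a longer listing. No new assessments are needed. SAP Section 5 says Part B had not begun and would be placed at a new site, so the change can be made with the other revisions for that move.

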#### **8.1.6 Interim Analyses**

No interim analyses are planned for this study; however, based on a review of the results from cohorts in the Dose Selection Phase in Part A, low, intermediate, and high doses of nalbuphine will be selected by the DRC for the Treatment Phase in Part B. Therefore, dose selection decisions and conclusions made by the DRC will be documented and included in the appendix of the CSR.

#### **8.1.7 Missing Data**

For PD and PK analyses, missing data for subjects who are administered all scheduled study treatments for all the treatment sessions will be considered as random non-informative missing for analysis purposes. Missing values will be examined on a case-by-case basis. Further details on missing values imputation for descriptive statistics and endpoints derivations will be provided in the SAP.

#### **8.1.8 Demographics and Other Baseline Characteristics**

For Part A and Part B, demographics and baseline characteristics (age, sex, race, ethnicity, recreational drug and alcohol use history, body weight, height, and BMI) will be summarized using descriptive statistics (number of subjects, mean, SD, minimum, median and maximum for continuous variables, and the proportion of subjects for categorical variables) for the Randomized population. No formal statistical comparison between the groups will be performed.

Medical history will be listed by subject. Medical history will be coded into the most recent version of MedDRA available (version 20.0 or later).

Prior and concomitant medications will be coded using the most recent version of the World Health Organization drug codes available (WHO Drug). Prior and concomitant medications will be listed by subject. The incidence of concomitant antiemetic medication use in will be tabulated by cohort (ie, dose level) and treatment (active drug or placebo) for Part A and by treatment for Part B.

The number of subjects in each treatment group will be presented, in addition to the number of subjects who complete each visit. The reasons for all post-randomization discontinuations will be tabulated and grouped by treatment and major reason. All deviations related to study inclusion or exclusion criteria, conduct of the trial, subject management, or subject assessment will be described.

## **8.2 Determination of Sample Size**

In Part A, cohorts of 8 subjects in a ratio of 6:2 nalbuphine:placebo will be considered a sufficient sample size for the Dose Selection Phase based on dose escalation paradigms used historically for HAP studies. The proposed single doses of nalbuphine solution for the first cohort will be 81 mg (equivalent to 90 mg of the HCl salt). Dose escalation will only occur for each subsequent cohort if an MSD has not been identified and the previous dose level was deemed to be safe and well tolerated. Escalation to the next dose level will continue until the maximum safe dose is identified or the highest proposed dose level of nalbuphine is achieved. Additional cohorts of 8 subjects may be added if a given dose level will be repeated to provide additional data or if a dose level, intermediate to those proposed, needs to be considered for safety or tolerability reasons.

In Part B, 56 healthy male and female subjects with a history of recreational opioid drug use will be enrolled in the Treatment Phase, with the intent to complete 42 subjects.

The sample size calculation was conducted based on unpublished Drug Liking VAS  $E_{max}$  (bipolar scale) data collected at the investigational site, which included hydromorphone 8 mg as the investigational positive control. Based on this data, the mean paired difference between hydromorphone and placebo was 24.6. Within-group SDs were 18.4 for hydromorphone and 18.0 for placebo. As determined by a published algorithm, adjusting for 7 periods and 14 sequences, with a 1-sided significance level of 0.05 and  $\delta_1 = 11$ , a sample size of 42 subjects will have at least 90% power to detect a difference in Drug Liking VAS  $E_{max}$  (bipolar scale). Assuming an approximate 25% dropout rate, 56 subjects (4 subjects per sequence) will be randomized into the Treatment Phase, with the intention to complete approximately 42 subjects (3 subjects per sequence).

## 9. STUDY ADMINISTRATION

### 9.1 Study Identification Card

Eligible subjects will be given a study identification card during the Qualification Phase (Part B) that confirms they are participants in a research trial with hydromorphone, nalbuphine solution, and an investigational drug.

Subjects will be provided with immediate medical care contact information that can be used during out-patient days between treatments. The card should contain trial site contact information (including direct telephone numbers) to be utilized in the event of an emergency. Subjects should be instructed to carry the card with them at all times until the end of their participation in the study.

### 9.2 Data Collection and Electronic Data Capture

The investigator or designee will record all required subject data using the specified data collection method agreed upon by INC Research Toronto, Inc. and Trevi Therapeutics, Inc. (ie, paper source and/or the electronic data capture [EDC] system).

The study site will use a validated EDC system to enter subject data onto electronic case report forms (eCRFs). Data will be collected using the EDC system and entered into a quality controlled clinical database. Prior to the commencement of the study, items to be included in the clinical database will be determined and suitable paper source documents will be created to ensure the appropriate collection of all required data. Clinical staff conducting the study will enter the required data onto source documents and generally different staff (who have been trained to do so) will enter the data from source documents into the clinical database, although there may be some staff overlap. All entries, corrections, and alterations will be made by the investigator or other authorized study personnel, and all data entries will be verified for accuracy and correctness. The EDC system is optimized for manual keying and review (including review by independent monitors) and maintains a full audit trail.

For subjects who do not qualify for the Treatment Phase of the study, demographic data collected during the Screening and Qualification visits will be entered into the clinical database.

Clinical laboratory and/or PK data will be transmitted electronically from external vendors to INC Research Data Management and reconciled against the clinical database. PsychometRx™ data will be captured electronically and imported into the clinical database.

The study file and all source data will be retained at the clinical site until notification is given by the sponsor for destruction.

